**Objective**

The primary objective of the proposed study is to evaluate the safety and efficacy of Brexpiprazole in adults with borderline personality disorder (BPD). Eighty subjects with BPD will be randomized in a 1:1 fashion to either Brexpiprazole (starting at 1mg/day for one week and going to 2mg in a fixed dose fashion after 1 week) or matching placebo for 12 weeks of active treatment. The hypothesis to be tested is that Brexpiprazole will result in greater rates of reduction in symptoms of BPD compared to placebo (improvement in symptoms will be indicated by lower scores on established outcome measures of BPD symptoms that have been used in prior studies).

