### **Subjects**

#### *Inclusion criteria:*

- 1) Men and women age 18-65;
- 2) Primary diagnosis of BPD
- 3) Zanarini scale score of at least 9 at baseline
- 4) Ability to understand and sign the consent form.

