### **Randomization**

Participants are randomized (1:1) to receive placebo or brexpiprazole by the investigational pharmacy at the University of Chicago. The study blind will be maintained by over-encapsulation, making placebo and active treatments appear identical in size, weight, shape, and color. Dosage changes and reductions will not be permitted during the study and participants will be discontinued if they experienced intolerance.

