#### *Assessments at each visit*

Those subjects who appear appropriate for the study, based on telephone screening, will be invited for a baseline assessment. The duration of the baseline assessment will be approximately 90 minutes and will include the following: Informed consent, Demographic data, Concomitant medications (no psychotropic medications will be allowed), Family history data, Medical evaluation including physical examination, EKG, weight, and vital signs, Urine pregnancy test (for women of childbearing years) and urine drug screen, and a psychiatric evaluation (using the following measures: MINI International Neuropsychiatric Interview (40); Depressive symptoms will be rated with the 24-item Hamilton Depression Rating Scale (HAM-D) (41); Anxiety

symptoms will be assessed using the Hamilton Anxiety Rating Scale (HAM-A) (42); Psychosocial functioning will be evaluated using the patient-rated version of the Sheehan Disability Scale (SDS) (43); Quality of Life Inventory (QOLI) (44); The Cambridge-Chicago Compulsivity Trait Scale (CHI-T); and the Columbia Suicide Severity Rating Scale (C-SSRS)). During the consent process, individuals will be given time to review the consent form and given the opportunity to ask any questions that may arise before signing the informed consent form. Throughout the study, subjects will be asked questions about the study to ensure that they continue understanding study procedures. Blood samples will be collected at both baseline and last visits to measure blood sugar, glutathione, and cholesterol levels. All follow-up visits will include safety measures (adverse events, vital signs, C-SSRS), weight, BPD measures, and other psychiatric measures.

Due to the pandemic of COVID19, study participants can perform their baseline and follow-up visits online using encrypted Zoom instead of in person visits. All inventories will be assessed. Blood samples and urine toxicology, however, will be at the discretion of the study PI. In cases where they are considered medically necessary, the participant can have them drawn locally and submitted to the study team.

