### **Efficacy evaluation:**

The primary outcome measure will be the change from baseline using the Zanarini Rating Scale for Borderline Personality Disorder (“Zanarini scale”) (45). This semistructured interview has anchored ratings (0=no symptoms, 4=severe symptoms) on nine items that correspond to the DSM-5 BPD criteria. Its subscales will be considered secondary efficacy measures.

Secondary efficacy measures include Modified Overt Aggression Scale (46), the Young Mania Rating Scale (47), and the self-report version of the Zanarini scale (48), the Borderline Evaluation of Severity Over Time (49), the Barratt Impulsiveness Scale (50) the Minnesota Impulsive Disorders Interview (51), the Symptom Checklist–90–Revised (SCL-90-R) (52), and the scales listed above (41-44).

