### **Data Analysis**

Data analysis will involve all visits during the 12-week double-blind treatment phase (up until week 12). Data from the tapering phase (weeks 12-13), although collected, will not be included for purposes of the primary goal of this study.

All enrolled subjects will be included in the analyses of baseline demographics and safety according to an intent-to-treat (ITT) principle. For statistical analysis, the full-analysis set will be defined as all participants who took at least 1 dose of the study drug and had at least 1 post-baseline primary efficacy assessment. The safety-analysis set will be defined as all randomized participants who took at least 1 dose of the study drug and completed at least 1 follow-up safety assessment.

The statistical model will be a linear mixed-effects regression model (LME) that includes terms for treatment group, time, and treatment-by-time interaction. The analyses will run using the nlme package on R for Windows (R Foundation, Vienna, Austria; <http://www.r-project.org>). Literature suggests LME without imputation may provide more accurate and stable results than LME models using fixed and multiple imputation methods for handling missing data, so no imputation will be undertaken for missing data. All tests of hypotheses will be performed using a two-sided significance level of 0.05.

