### **Sample Size**

The sample size was calculated for the primary endpoint of change from baseline. Assuming a similar magnitude of effect seen in other studies of medications for BPD, it was determined that 40 participants would be needed in each treatment group to detect a difference with an overall 5% type-I error risk. Given the particularly low rates of adverse events reported with Brexpiprazole, as well as its more positive side effect profile in terms of sexual side effects, we expect few drop-outs from the study and therefore a smaller sample is needed.

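### The primary model names no baseline Zanarini adjustment for a change-from-baseline endpoint, which generally gives up precision if the contrast is change at a visit

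*Combined protocol and SAP*

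**What the plan says.** The Efficacy evaluation section states: "The primary outcome measure will be the change from baseline using the Zanarini Rating Scale for Borderline Personality Disorder". The Sample Size section agrees: "The sample size was calculated for the primary endpoint of change from baseline". The Objective is worded differently, as a hypothesis about pace: "Brexpiprazole will result in greater rates of reduction in symptoms of BPD compared to placebo".

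The only description of the primary model is in Data Analysis: "The statistical model will be a linear mixed-effects regression model (LME) that includes terms for treatment group, time, and treatment-by-time interaction". The same section adds: "Data analysis will involve all visits during the 12-week double-blind treatment phase". It rules out imputation and sets a two-sided 0.05 level.

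The baseline score will exist, because the inclusion criteria require "Zanarini scale score of at least 9 at baseline". It is then followed over time: "All follow-up visits will include safety measures (adverse events, vital signs, C-SSRS), weight, BPD measures, and other psychiatric measures". The Randomization section says "Participants are randomized (1:1) to receive placebo or brexpiprazole by the investigational pharmacy" and describes no stratification.

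No section mentions a baseline covariate, a baseline-by-time term or equal arm means at baseline. The documents also do not say whether baseline is a row of the response or is only subtracted, whether time is categorical or linear, what the covariance is, or which contrast is primary.

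**The concern.** A raw change score subtracts the whole baseline value. When baseline and follow-up are imperfectly correlated, that usually removes too much, and the change carries baseline noise that a regression on baseline would take out. What the named terms cost depends on choices the plan leaves open:

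- **(a) Contrast is change at a visit.** The named terms give an unadjusted comparison of change scores.
- **(b) Baseline is the first repeated response, with linear time.** A free treatment main effect lets the arms differ at week 0, although randomisation makes their true means equal.
- **(c) Contrast is a slope of post-baseline change only.** Subtracting baseline shifts every visit alike, so adjustment may gain nothing.

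Under (a), and usually under (b), the primary confidence interval is wider than the collected data allow. A chance baseline difference also moves the estimate in this one trial through regression to the mean. With 40 per arm and no stated power, the plan shows no precision to spare.

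**Working it through.** **Inputs.** From the documents: 80 participants randomised 1:1, 40 per arm, two-sided 0.05, Zanarini at least 9 at baseline. Visits are taken at weeks 0, 1, 2, 4, 6, 8, 10 and 12 (Study Design/Methodology). Treatment Duration allows weekly visits for 2 to 4 weeks, so adding week 3 was also tried. Assumed, because not given: correlation rho, SDs, covariance and dropout.

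**Step 1: the plan's own figure.** The 40 per arm cannot be reproduced, because no effect size, SD or power is stated. Back-solving, it matches a standardised difference of (1.960 + 0.842) × √(2/40) = 0.626 at 80% power, or 0.725 at 90%.

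**Step 2: case (a), equal SDs.** In units of s², with n = 40:

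- unadjusted variance = (2/n) × 2(1 − rho)
- adjusted variance = (2/n) × (1 − rho²)
- ratio adjusted/unadjusted = (1 + rho)/2
- shift from a 1-SE chance baseline difference (√(2/40) = 0.22 SD) = (1 − rho) × 0.22, which is √((1 − rho)/2) of the unadjusted SE

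| rho | ratio | variance given up | 95% CI half-width, SD | shift, SD | shift / SE |
|---|---|---|---|---|---|
| 0.3 | 0.65 | 35% | 0.53 to 0.42 | 0.16 | 0.59 |
| 0.5 | 0.75 | 25% | 0.45 to 0.39 | 0.11 | 0.50 |
| 0.7 | 0.85 | 15% | 0.34 to 0.32 | 0.07 | 0.39 |
| 0.8 | 0.90 | 10% | 0.28 to 0.27 | 0.04 | 0.32 |

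Half-widths use t on 78 and 77 df. They are before the cost of estimating the covariate, about 1 + 1/(80 − 4) = 1.013 in variance.

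**Step 3: case (a), narrower baseline.** The cut-off of 9 can truncate the baseline distribution. If a standard normal baseline is cut at c, its variance is v = 1 + cL − L², with L = pdf(c)/sf(c). The ratio is (1 − rho²)/[v(1 − rho)² + 1 − rho²], with rho the correlation before truncation.

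- Cut-off 1 SD below the mean: v = 0.630, ratios 0.83 and 0.90 at rho 0.5 and 0.7.
- Cut-off at the mean: v = 0.363, ratios 0.89 and 0.94.

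The loss is therefore 6% to 17%. More generally, with k = baseline SD / week-12 SD, the ratio is (1 − rho²)/(1 + k² − 2·rho·k). At k = 0.7 this gives 0.85, 0.95 and 1.00 at rho 0.3, 0.5 and 0.7. The loss vanishes when rho = k.

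**Step 4: slopes.** The generalised least squares variance of treatment-by-time was computed with and without a free treatment effect at week 0 (case b). For case (c) it was computed with and without conditioning on baseline by visit. The random intercept/slope/residual variances were 0.6/0.003/0.4, 0.5/0.005/0.5 and 0.5/0.0025/0.5.

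| assumed structure | ratio (b) | ratio (c) |
|---|---|---|
| random intercept and slope, uncorrelated | 0.90–0.94 | 1.00 |
| same, correlation −0.3 | 0.77–0.81 | 0.98 |
| same, correlation +0.3 | 0.98–1.00 | 0.98 |
| compound symmetry 0.3, 0.5, 0.7 | 0.72, 0.84, 0.92 | 1.00 |
| AR(1) 0.95, 0.90 per week | 0.77, 0.63 | 0.80, 0.72 |

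Adding week 3 changes (b) little: 0.91–0.95 with uncorrelated random slopes and 0.74–0.93 under compound symmetry.

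**Step 5: validity.** In 40,000 simulated complete-data trials of case (a) with no effect, type I error was 0.048–0.050 unadjusted and 0.047–0.051 adjusted. With a true effect of −0.50, both methods averaged −0.497 to −0.500. With about 20% dropout that depended on baseline in the active arm only, the change-score estimate without baseline averaged −0.35 at rho 0.26 and −0.40 at rho 0.5.

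**Step 6: the constraint under linear time.** Suppose treatment produces an immediate constant difference of −0.5 SD. Under compound symmetry 0.3–0.7, the fitted slope difference over 12 weeks is −0.24 with the free week-0 term and −0.45 to −0.30 with a common baseline. The constraint changes the estimate as well as its variance.

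**The case against.** The strongest reply has four parts.

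1. **The list of terms is not closed.** The sentence says what the model includes, so a baseline term is not excluded. That is true, but nothing says one will be added, and the choice should be made before the data are seen.

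2. **The Objective speaks of rates, and the model's treatment-by-time term fits a slope.** For a slope the gain can be slight: a ratio of 0.90–0.94 with uncorrelated random slopes (an interval about 3–5% narrower), and 1.00 in several versions of (c). This stands, and it is why the point is conditional on the contrast. But two sections define the endpoint as change from baseline, so change at a visit is at least as natural a reading.

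3. **A common-baseline constraint is not purely an efficiency gain.** This also stands. Step 6 shows it alters the slope estimate when the arms do not diverge in a straight line from week 0. The regimen has a dose step after the first week, so straight-line divergence is not assured.

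4. **An unadjusted randomised comparison is valid, and the study calls itself a pilot.** This stands as to validity. It does not make the lost precision worth losing when recovering it costs a sentence or two.

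A reader might infer that the plan throws away some 37% of the variance. The slope calculation reaches that figure only under AR(1) at 0.90 per week, a structure the documents never name. Nor is it a ceiling: equal SDs and a correlation of 0.2 give (1 − 0.2)/2 = 40% for change at a visit.

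**Conclusion.** The omission is real, and its consequence is mainly a loss of efficiency. For change at a visit, precision is generally given up: 10–35% of the variance at correlations 0.8 to 0.3 with equal SDs, 6–17% at correlations 0.7 to 0.5 with a truncated baseline, and none when the correlation equals baseline SD divided by follow-up SD. For a linear slope with baseline as a response, the loss is about 6–10% with uncorrelated random intercept and slope, and from almost nothing to over 20% under other structures. For a slope of post-baseline change it is often nil. All of these rest on assumed correlations, SDs and covariances, and none is a bound for this trial.

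A reader might also infer that the primary test is biased or its error rate inflated. The documents do not support that: with complete data, or data missing at random given what the model contains, the comparison is valid and unbiased on average. The exception is a change-score model with baseline nowhere in it, which can be biased if dropout depends on baseline differently by arm. Nothing in the documents shows that this will happen; the Sample Size section expects few drop-outs. Nor does the point show that 40 per arm is wrong, since that figure can be neither confirmed nor refuted.

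**What to change.** In the Data Analysis section, state the primary contrast and how baseline enters, choosing one form in advance.

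- **If the contrast is change at a visit:** name the visit. Model post-baseline change with treatment, visit (categorical), treatment-by-visit, baseline Zanarini score and baseline-by-visit. An essentially equivalent form keeps baseline as a response, with categorical time, an unstructured covariance and a common baseline mean in both arms.
- **If a linear-time slope is intended:** say so, and say whether baseline is a response. Do not impose the common-baseline constraint automatically. It assumes straight-line divergence from week 0 and should be adopted only if the sponsor is willing to defend that shape.

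The cost is one or two sentences and a few degrees of freedom, about 1.3% of variance for one covariate with 80 participants. Where adjustment gains nothing, that is the whole loss. No new Zanarini data, visits or participants are needed. If 40 per arm gave 80% power for the unadjusted change (an assumption), recovering 15% or 25% of the variance would raise power to about 86% or 90%.

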### **Study Design/Methodology**

Eighty individuals with a prior diagnosis of BPD will be recruited for a double-blind, placebo-controlled pilot study in which Brexpiprazole or placebo is administered in a 1:1 fashion. All 80 subjects will have current BPD per DSM-5 criteria. Following baseline measures, subjects will receive Brexpiprazole (1mg/day for one week and then 2mg/day thereafter) or inactive placebo. Participants will be seen every week for the first 2 weeks and then every 2 weeks after that. At week 12, subjects will start a 1-week taper off the medication. Efficacy and safety measures will be performed at each visit.

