### **Treatment Duration, Visit Frequency, and Procedures**

This is a 13-week study (12 weeks of acute treatment followed by a 1-week tapering phase). Subjects will be seen at baseline and then every week for the first 2-4 weeks and then every two weeks after that.

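### Do the unstated time coding, random effects and time point of change leave the primary Zanarini test open enough to need an amendment?

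*Combined protocol and SAP*

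**What the plan says.** The Objective section states: "The hypothesis to be tested is that Brexpiprazole will result in greater rates of reduction in symptoms of BPD compared to placebo". That is the language of a rate.

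The Efficacy evaluation section states: "The primary outcome measure will be the change from baseline using the Zanarini Rating Scale for Borderline Personality Disorder". No visit is named for the change. The Sample Size section uses the same quantity: "The sample size was calculated for the primary endpoint of change from baseline". It gives 40 per group and a 5% type I error, but no effect size, standard deviation, power or time point.

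The Data Analysis section names a "linear mixed-effects regression model (LME) that includes terms for treatment group, time, and treatment-by-time interaction". It adds the nlme package in R, visits up to week 12 with the taper left out, no imputation, and two-sided 0.05. It does not say whether time is a number or a factor, and it gives no random effects or within-subject covariance.

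On visits, Study Design/Methodology states: "Participants will be seen every week for the first 2 weeks and then every 2 weeks after that". Treatment Duration, Visit Frequency, and Procedures states: "Subjects will be seen at baseline and then every week for the first 2-4 weeks and then every two weeks after that".

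**The concern.** One line of model description covers at least three different tests of the same data: a 1-df difference in slopes, an omnibus interaction over all post-baseline visits (7 df with eight visits), and the week-12 difference in change. The hypothesis leans to the first, while the endpoint and sample size lean to the last. If the choice were made after the results were seen, the 5% level would not hold.

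Even without such a choice, a linear-time model fitted with a random intercept only treats subjects' slopes as equal. If they are not, its standard error for the slope difference is too small. The two visit schedules also leave the number of time points at eight or up to nine.

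**Working it through.** **Inputs.** From the documents: 40 per arm, 1:1, two-sided 0.05, and visits at weeks 0, 1, 2, 4, 6, 8, 10, 12 (Study Design/Methodology) or up to 0, 1, 2, 3, 4, 6, 8, 10, 12 (Treatment Duration). Assumed, because the documents do not give them: no dropout, the covariance, and the size and shape of the effect. Six covariances were used:

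- compound symmetry, correlation 0.5 or 0.7
- intercept variance 0.5, residual variance 0.5 and slope SD 0.03 or 0.05 per week
- serial correlation of 0.8 at 4 weeks
- intercept variance 0.3, serial variance 0.4 (correlation 0.6 at 4 weeks) and residual variance 0.3

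**1. The plan's own figure.** The 40 per arm cannot be reproduced forward. Solved backward, d = (1.960 + z_power) × √(2/40). At 80% power this is 2.802 × 0.2236 = 0.63; at 85% it is 0.67 and at 90% it is 0.72. With 40 per arm, power is 43% for d = 0.4, 61% for 0.5, 77% for 0.6 and 95% for 0.8. So power is unknown whichever test is named.

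**2. Hand check, compound symmetry, residual variance s².** Mean visit time is 43/8 = 5.375 and Sxx = 365 − 8 × 5.375² = 133.875.

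- Variance of the week-12 change difference: 2 × 2s²/40 = 0.100s².
- Variance of 12 × the slope difference: 144 × 2s²/(40 × 133.875) = 0.0538s².
- SE ratio: √(0.100/0.0538) = 1.364.
- Linear effect worth 80% at week 12 (z = 2.802): slope z = 2.802 × 1.364 = 3.82, power Φ(3.82 − 1.96) = 97%.
- Effect complete by week 2 (shape 0, 0.5, then 1): fitted slope × 12 = 12 × 7.5625/133.875 = 0.678 of the full effect, so z = 3.82 × 0.678 = 2.59 and power is Φ(0.63) = 74%.

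**3. Range over the six covariances** (effect set for 80% power at week 12, covariance known):

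| Effect shape | Slope | Omnibus, 7 df | Week 12 |
|---|---|---|---|
| Linear to week 12 | 80–97% | 49–81% | 80% |
| Complete by week 6 | 80–98% | 78–92% | 80% |
| Complete by week 2 | 63–79% | 83–100% | 80% |

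Fitting the slope with random intercept and slope gives 76–97% for the linear shape and 44–74% for the week-2 shape. The three tests are not unanimous in 20–34% of trials with a true effect. Slope and week 12 alone disagree in 0.3–21%.

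**4. Type I error, covariance estimated.** Random intercept plus slope (78 df) rejects in 4.1–5.2% of null trials, and the week-12 contrast (78 df) in 4.8–5.1%. The omnibus test rejects in 4.7–5.0% on F(7,72), but in 8.4–8.9% if residual degrees of freedom, F(7,624), are used.

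Random intercept only, by hand, for slope SD 0.05 and residual variance 0.5:

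- True per-subject slope variance: 0.0025 + 0.5/133.875 = 0.00624.
- Variance the model assumes: (0.5 + 0.0025 × 133.875/7)/133.875 = 0.00409.
- Type I error: 2[1 − Φ(1.96 × √(0.00409/0.00624))] = 2[1 − Φ(1.59)] = 11%.

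The same sum with slope SD 0.03 gives 7%. Simulation gives 5% under compound symmetry, 7–11% with varying slopes and 17–33% under the two serial structures. Other assumed variances (residual 0.4, slope SD over 12 weeks 0.6–0.8) give 13–18%.

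**5. Choosing after the results.** Slope or week 12: 5.1–8.2%. Any of the three: 8.9–11.5%. No section of the plan provides for this.

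**6. Visit grid.** With nine visits instead of eight, omnibus power for a linear effect is 47–80% against 49–81%. The largest shift found for the slope, omnibus or week-12 test is in slope power with a week-2 plateau, for example 60% to 53%. Slope power for a linear effect changes by less than 1 point.

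**The case for a change.** The strongest case for a change is that the text cannot be made to yield one test. The week-12 limit sets a data window, not a contrast. Naming nlme fixes the software, not the model. An analyst could fit a random intercept alone without departing from a word of the plan, and could then have a type I error well above 5% with no post-hoc choice at all. One added sentence would cost no patients or visits.

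The omission stands, and so does the warning about a random intercept alone. Three things weaken the step to an amendment.

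- The plan does not prescribe the faulty model, and allowing for subject-specific slopes or serial correlation is ordinary practice in the named package. The 7–33% range also rests on invented covariances; its upper end needs pure serial correlation with no measurement error.
- A rate of reduction is not naturally a 7-df omnibus hypothesis. With linear time, the 12-week difference in change is 12 times the slope difference, so rate and change are largely two descriptions of one quantity. Disagreement between valid tests is not an error rate.
- Tighter wording is not automatically safer. With no treatment effect, nlme's default fit of random intercept and slope failed in 61 of 200 simulated trials without slope variance, 18 of 200 at slope SD 0.03 and 1 of 200 at 0.05, so a fallback would be needed. An unweighted t-test of per-subject slopes drops from 75–97% power to 45–64% with one week-1 leaver per arm. For the week-12 contrast, a continuous-time autoregressive fallback without a random intercept has 21–60% power and 0.03–1.1% type I error in five of the six covariances.

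**Conclusion.** No change to the plan follows. This is missing detail that an analyst can fill sensibly: the outcome, the interaction, the analysis window and the two-sided 5% level are all stated, and the Objective and Data Analysis sections point the same way. Each candidate test holds about 5% when fixed before unblinding and fitted with a suitable covariance and degrees of freedom.

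The choice between a slope and a week-12 contrast is a fair trade-off. Fitted with random slopes, the slope test gains up to 17 points (97% against 80%) if the effect grows linearly. It loses up to 36 points (44% against 80%) if the effect is complete by week 2. Nothing in the documents says which shape to expect. Naming the test would not make power verifiable either, because the Sample Size section gives no effect size, SD or power. The two visit schedules read as a drafting slip that moves power by at most about 7 points.

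These figures assume 40 per arm, no dropout and the covariances listed; they illustrate sensitivity and do not estimate this trial's power. The conclusion would differ if the plan prescribed linear time with a random intercept alone, or left the choice of test until after the results were seen. It does neither.
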